
STATISTICAL METHODS
	
Sample size:
 
Patients will be treated with PM060184 to test the null hypothesis (H0) that 30% or less patients are alive and free of progression at 12 weeks (PFS3) according to RECIST v.1.1 ($p \leq 0.30$) versus the alternative hypothesis (H1) that 50% or more patients are alive and free of progression at twelve weeks according to the aforementioned criteria ($p \geq 0.50$). The variance of the standardized test is based on the null hypothesis. The type I error (alpha) associated with this one-sided test is 0.025 and the type II error (beta) is 0.1; hence, statistical power is 90%.
 
Sixty evaluable patients are necessary to test the hypothesis. A futility analysis using O'Brien-Fleming boundaries is planned when 24 patients can be evaluated (first stage). If there are seven or more patients achieving PFS3 in the first stage then the trial will proceed to a second stage and a total of 60 patients will be recruited.
 
If at least 25 of 60 evaluable patients are alive and free of progression at 12 weeks then the null hypothesis can be rejected and PM060184 considered active and deserving potential development in this setting.
 
Primary endpoint:
 
 • PFS3, defined as the percentage of patients remaining alive and progression-free at Week 12 (Month 3) after the first treatment dose. 
Secondary endpoints:
 
 • Overall survival (OS), defined as the time from the first day of treatment to the date of death or last contact. • Progression-free survival (PFS), defined as the time from the first day of study treatment to the day of assessment of progression, death or last tumor evaluation. • Overall response rate (ORR), defined as the percentage of patients with either complete response (CR) or partial response (PR) according to RECIST v.1.1. • Duration of response (DOR), defined as the time between the date when response criteria (PR or CR, the first to be reached) are fulfilled and the first date when PD, recurrence or death is objectively documented. • Treatment safety, including AEs, SAEs and laboratory abnormalities graded according to NCI-CTCAE v.4. Dose reductions or delays due to treatment-related AEs, and reasons for treatment discontinuations will also be analyzed. • PN and QoL profiles as reported by patients using the EORTC QLQ-CIPN20 and QLQ-C30. • PK parameters will be evaluated in plasma by population PK

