6.3.4 Replacement of Patients

Patients must be replaced if they are considered not evaluable for efficacy for the primary endpoint (PFS3), i.e., if they are withdrawn from the study due to significant clinical deterioration of unknown reason, hypersensitivity reactions, unrelated AEs without any tumor assessments after the start of study treatment, if they receive less than one complete treatment cycle (at least two PM060184 dose administrations over two cycles unless treatment discontinuation was due to unmanageable toxicity), or do not have the disease assessment at Week 12 (except in the case of treatment discontinuation/death due to a treatment-related AE, symptomatic deterioration due to the disease, clinical progression, PD or death due to malignant disease).

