8. STUDY EVALUATIONS

8.1 EFFICACY

Patients will be evaluable for efficacy if they receive at least one complete treatment cycle (or two PM060184 dose administrations over two cycles) and have, at least, one disease assessment at Week 6 and another one at Week 12.

In addition, any patient who presents disease progression, symptomatic deterioration due to the disease or clinical progression, dies due to malignant disease, discontinues treatment due to unmanageable toxicity, or dies or discontinues treatment due to a treatment-related AE before evaluation of the response at Week 12 will also be considered evaluable for the primary endpoint and classified as a non-responder.

Patients who have no disease assessment at Week 6 but remain on treatment and are assessed at Week 12 (or later, and with no evidence of disease progression) will be considered evaluable for efficacy.

Patients who refuse further treatment before Week 12 due to reasons other than related AEs not considered unmanageable toxicity will be replaced.

A futility analysis will be performed once the first 24 evaluable patients complete the Week 12 (\pm 5 days) tumor assessment; progress; die due to PD; or discontinue treatment due to unmanageable toxicity (whichever occurs first). If seven patients or more achieve PFS3, then 36 additional patients will be recruited (second stage).

Tumor assessment will be measured using RECIST v.1.1 ([17](#)).

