9. STATISTICAL METHODS

9.1 PRIMARY ENDPOINT

Progression-free survival rate at 12 weeks (PFS3), defined as the rate estimate of the percentage of patients who are alive and progression-free at 12 weeks (~3 months) after the first treatment administration.

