4. PATIENTS EVALUABILITY CRITERIA

Patients with relapsed, metastatic/locally advanced CRC with any KRAS-mutation status (wild-type, mutated, or status unknown), progressing after standard treatments (fluoropyrimidine, irinotecan, and oxaliplatin).

Patients must fulfill all the eligibility criteria to be eligible to participate in the study.

The study will include the following analysis population set definitions:

- “All Included Patients” analysis set is defined as all patients recorded in the database who have been included in the trial (excluding screening failures), independently of whether they have received the study drug or not.
- “All Treated Patients” analysis set is defined as all included patients who have received at least one (complete or incomplete) dose of the study drug.
- “All Evaluable Patients for Efficacy” analysis set is defined as all eligible patients who have at least one complete treatment cycle (or two PM060184 dose administrations over two cycles) and have, at least, one disease assessment at Week 6 and another one at Week 12. In addition, any patient who presents disease progression, symptomatic deterioration due to the disease or clinical progression, dies due to malignant disease, discontinues treatment due to unmanageable toxicity, or dies or discontinues treatment due to a treatment-related AE before evaluation of the response at Week 12 will also be considered evaluable for the primary endpoint and classified as a non-responder. Patients who have no disease assessment at Week 6 but remain on treatment and are assessed at Week 12 (or later, and with no evidence of disease progression) will be considered evaluable for efficacy. Patients who refuse further treatment before Week 12 due to reasons other than related AEs not considered unmanageable toxicity will be replaced.

- “All Responder Patients” analysis set is defined as all evaluable patients for efficacy who have had CR or PR as overall best response according to the RECIST v.1.1.
- “All Evaluable Quality of Life (QoL)” analysis set is defined as all patients who have fulfilled the EORTC-QLQ-C30 and EORTC-QLQ-CPIN20 questionnaires for at least two timepoints, one at baseline and at least one after the start of the therapy.

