4.2. Efficacy Populations

The “All evaluable patients for efficacy” analysis set will be used for the primary endpoint analysis of PFS3 and secondary endpoint analyses of OS, PFS and ORR.

The secondary endpoint analysis of DOR will be based on the “All responder patients”.

The “All evaluable QoL” set will be used for the secondary endpoint analysis of changes in patients QoL.

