8.12. Subgroup Analyses

If applicable, specific analyses for different subgroups determined by the following factors will be developed: prior oxaliplatin exposure, tumor primary location: right vs left side tumors, KRAS status, BRAF-like expression, MSI phenotype and other relevant factors determined by the oncologist.

No differentiation by center is planned.

8.13. *Methods for Handling Missing Data*

Missing values will not be included in the calculation of outputs.

8.14. *First Stage Analysis*

A futility analysis will be performed once the first 24 evaluable patients complete the Week 12 (± 5 days) tumor assessment; progress; die due to PD; or discontinue treatment due to unmanageable toxicity (whichever occurs first). If seven patients or more achieve PFS3, then 36 additional patients will be recruited (second stage).

8.15. *Identification of Fixed or Random Effects Models*

Not applicable.

8.16. *Data Analysis Conventions*

All data analysis conventions, data calculations and grouping needed to perform the statistical analysis will be described in a separate document.

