10.2.1. Treatment discontinuations

Table 10.2.1 Treatment discontinuation.

Reason	N	%
Progressive disease		
Patient refusal to treatment		
Death (due to toxicity)* ¹		
Death (non-treatment-related)* ²		
Investigator's decision* ³		
Treatment-related AE		
Non treatment-related AE		
Other* ³		
Total		

(*¹) Cause of death = Study drug related AE; (*²) Cause of death = Malignant disease, Non study drug related AE or Other; (*³) See [Listing 10.2.2](#).

Listing 10.2.2 Reasons for treatment discontinuation other than progressive disease.

Patient id.	Reason	Last cycle	Comments

When the reason for discontinuation is a study treatment-related adverse event or death due to toxicity, patients will be identified and described in depth in [Listing 10.2.3](#).

Listing 10.2.3 Treatment discontinuation due to AEs.

Patient id.	Last cycle	Preferred term code	AE reported (verbatim)	Grade	Relationship	Onset date	Resolved date	Seriousness criteria

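### Patients who die before Week 12 of a cause that is neither malignant nor treatment-related are replaced, although the PFS3 definition makes them failures

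*Protocol*

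**What the plan says.** **Endpoint.** The protocol synopsis gives "PFS3, defined as the percentage of patients remaining alive and progression-free at Week 12 (Month 3) after the first treatment dose". Protocol 9.1 and SAP 3.3 use the same idea: the patient must be "alive and progression-free at 12 weeks (~3 months) after the first treatment administration". None of these distinguishes between causes of death.

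**Who is evaluable.** Without a Week 12 assessment, a patient becomes an evaluable non-responder only for a listed reason. Protocol 8.1 covers a patient who progresses or deteriorates from the disease, or who "dies due to malignant disease, discontinues treatment due to unmanageable toxicity, or dies or discontinues treatment due to a treatment-related AE before evaluation" of the Week 12 response. SAP 4 repeats the list, starting from "any patient who presents disease progression, symptomatic deterioration due to the disease or clinical progression, dies due to malignant disease". The only deaths on it are malignant or treatment-related.

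**Who is replaced.** Protocol 6.3.4 and the synopsis replace patients who "do not have the disease assessment at Week 12 (except in the case of treatment discontinuation/death due to a treatment-related AE", disease-related deterioration, clinical progression, PD or malignant death applies. SAP 4 has the same rule by reference to its own list.

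**Analysis.** SAP 4.2 states that the evaluable "analysis set will be used for the primary endpoint analysis of PFS3 and secondary endpoint analyses of OS, PFS and ORR". SAP 11.3.1 sets PFS3 = No for insufficient follow-up, but only in patients who are already evaluable. The first-stage analysis (Protocol 8.1, SAP 8.14) waits until the first 24 evaluable patients complete the Week 12 scan, "progress; die due to PD; or discontinue treatment due to unmanageable toxicity (whichever occurs first").

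**Decision.** Protocol 9.3: at least 7 of 24 to continue, at least 25 of 60 to declare activity, tested against a 30% null.

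**The concern.** The evaluability and replacement rules agree with each other but not with the endpoint. A progression-free patient who dies at, say, Week 8 of an unrelated cause is not alive at 12 weeks and has failed PFS3 by definition. Under the rules that patient is not evaluable, leaves the denominator, and is replaced by someone who may succeed.

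The SAP foresees such deaths: the footnote to Table 10.2.1 groups non-treatment-related deaths as "Cause of death = Malignant disease, Non study drug related AE or Other", and Table 12.3.6 tabulates the same causes.

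The trial has one arm and decides by a fixed count. Removing true failures moves that count in one direction only, and in an open-label trial the attributed cause of death settles whether a failure is counted. Because the same set serves the main OS analysis, these deaths also disappear from overall survival.

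**Working it through.** **1. The text, case by case.** A treated patient has no Week 12 assessment.

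| What happened before Week 12 | PFS3 definition | Protocol 8.1 / SAP 4 | Protocol 6.3.4 / SAP 4 replacement |
|---|---|---|---|
| PD, clinical progression or disease-related deterioration | failure | evaluable, failure | exempt from the Week 12 clause |
| Malignant death | failure | evaluable, failure | exempt from the Week 12 clause |
| Treatment-related death | failure | evaluable, failure | exempt from the Week 12 clause |
| Other death, no progression | failure | not listed, so not evaluable | replaced |

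Only the last row conflicts. SAP 11.3.1 does not rescue it, because that rule presupposes evaluability.

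**2. The plan's own figures (Protocol 9.3).** Inputs: p0 = 0.30, p1 = 0.50, one-sided alpha 0.025, power 90%, null variance in the test.

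- n = [1.960·√(0.30·0.70) + 1.282·√(0.50·0.50)]² / 0.20² = 59.2, so 60.
- Critical count = 60·(0.30 + 1.960·√(0.21/60)) = 24.96, so 25.
- At 25/60: z = (0.4167 − 0.30)/√(0.21/60) = 1.97, one-sided p = 0.024. At 24/60: z = 1.69, p = 0.045.

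The sample size and the cutoff both reproduce.

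**3. Exact chance of passing.** P(pass) = P(X1 ≥ 7 of 24 and X1 + X2 ≥ 25 of 60), X1 and X2 binomial with a common rate. At 0.30 this is 3.5%; at 0.50 it is 91.8%.

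**4. Effect of replacement.** Let k such deaths be replaced for every 60 evaluable patients, and let the true rate with those deaths counted be 30%. The 60 + k patients contain 0.30·(60 + k) successes, all of them in the evaluable set, so the evaluable-set rate is 0.30·(60 + k)/60. The documents give no rate for such deaths; k = 1 to 3 is an assumption.

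| k | Evaluable-set rate | Pass stage 1 (≥ 7/24) | Pass both stages |
|---|---|---|---|
| 0 | 0.300 | 61.1% | 3.5% |
| 1 | 0.305 | 63.2% | 4.3% |
| 2 | 0.310 | 65.2% | 5.1% |
| 3 | 0.315 | 67.1% | 6.1% |

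The gap between 3.5% and the nominal 2.5% at k = 0 comes from the normal approximation. It is a separate matter and is not charged to this point.

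**5. At the boundary.** Suppose the trial ends at exactly 25/60 with one such death replaced. Counting that death and keeping n = 60 means one replacement patient is not enrolled. If patients are exchangeable, that patient was a success with probability 25/60 = 42%, giving 24/60 (a fail), and a failure with probability 35/60 = 58%, leaving 25/60 (still a pass).

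**The case against.** **An evaluable-set analysis with replacement is a design choice.** It is stated consistently, and the decision rule is written for evaluable patients. That explains the set, but not why it departs from the endpoint definition for one class of death. It does mean that the figures above rest on reading the 30% null as applying with all such deaths counted.

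**The group is small.** This stands. SAP 12.2 and Table 12.2.1 treat AEs of unknown relationship as drug-related, and the study-discontinuation table (10.2.4) does so for deaths, although Table 10.2.1 does not repeat it. Disease-related deterioration already counts as failure. Entry requires ECOG 0 or 1 and life expectancy of at least three months.

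**An all-treated analysis exists.** A reader might infer that these deaths are never counted. That is not so: SAP 6.2.2 plans a Kaplan-Meier PFS sensitivity analysis in all treated patients with progression or death as the event, and Table 11.3.7 reports PFS at 3 months. It does not govern 7/24 or 25/60, and no all-treated binomial PFS3 or all-treated OS analysis is planned.

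**The first-stage wording only times the analysis.** Largely true. It classifies nobody and also omits treatment-related death, so it reads as shorthand. It needs aligning but is not a second error.

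**Overlap of the two lists.** A reader might infer that treatment-related hypersensitivity stops, or PD after less than one cycle, are also replaced. The literal wording of 6.3.4 allows that. But 6.3.4 applies to patients considered not evaluable, and 8.1 says its listed patients are evaluable in addition, so the documents support the conservative reading. This is a clarification only.

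**Conclusion.** The point holds for one narrow class: treated, progression-free patients who die before the Week 12 assessment of a cause that is neither malignant nor treatment-related. They are failures by definition, yet they leave the 7/24 and 25/60 counts and the main PFS and OS analyses. The bias in PFS3 can only be upward. On the assumption of 1 to 3 such deaths per 60 evaluable and a true rate of 30% with them counted, the chance of passing rises by about 0.7 to 2.5 percentage points from 3.5%.

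A reader might infer that a single such death turns a bare pass into a fail, by adding it to the denominator to give 25/61. The plan tests no such result: the decision is on 60 patients, and a death that is counted takes one of those places. A bare pass is then lost in about 42% of cases, assuming exchangeability.

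This should be fixed. The contradiction is certain from the text; its size depends on a death rate that the documents do not give.

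**What to change.** 1. In the synopsis, Protocol 6.3.4 and 8.1, and SAP 4, state that any treated patient with PD or death from any cause before the Week 12 assessment is evaluable, is PFS3 = No whatever the number of doses, and is not replaced. Include a patient who refused further treatment and is then known to have died before Week 12; otherwise leave the refusal rule as it is. Keep 60 evaluable patients and the 7/24 and 25/60 rules. Align the first-stage wording in the synopsis, Protocol 8.1 and SAP 8.14, which now names only death due to PD.
2. As a minor clarification, state that a patient who meets the non-responder rule is never replaced, and reconcile the hypersensitivity and less-than-one-cycle wording of the replacement rule with it.
3. Add to SAP 11.3.1 an exact-binomial PFS3 table in All Treated Patients, with unknown status taken as No, as a supportive analysis without a decision rule. Add an all-treated OS analysis.

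The cost is wording plus one or two tables. Sample size and visits do not change. The reported PFS3 figure may be slightly less favourable.

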6.4 PROTOCOL DEVIATIONS

A protocol deviation is defined as any departure from what is described in the protocol of a clinical trial approved by an Independent Ethics Committee (IEC)/Institutional Review Board (IRB) and the Competent Authorities. Therefore, it applies to deviations related to patient inclusion and clinical procedures (e.g., assessments to be conducted or parameters to be determined), and also to other procedures described in the protocol that concern Good Clinical Practice (GCP) guidelines or ethical issues (e.g., issues related to obtaining the patients' Informed Consent, data reporting, Investigator's responsibilities, etc.).

Deviations with no effects on the risk/benefit ratio of the clinical trial (such as minimal delays in assessments or visits) will be distinguished from those that might have an effect on this risk/benefit ratio, such as:

- Deviations that might affect the clinical trial objectives, such as those involving inclusion/exclusion criteria (which could mean that the patient is not eligible for the trial) and those having an effect on patient's evaluability.
- Deviations that might affect the patient's well-being and/or safety, such as incorrect dosing of the IMP due to not following dose adjustment specifications or an incorrect preparation of the medication.
- Deviations related to compliance with GCP guidelines as described in the protocol and regulations in force, such as deviations when obtaining the Informed Consent or not following the terms established for reporting Serious Adverse Events, etc.

As a general rule, NO deviations that may have an effect on the evaluation of the risk/benefit ratio of the study treatment will be authorized. All protocol deviations detected during the study will be appropriately documented, and those considered particularly relevant (i.e., those related to ethical issues, fulfillment of GCP guidelines and with an effect on the evaluation of the risk/benefit ratio) will be notified to the pertinent IEC/IRB and, if applicable, to the Competent Authorities as established by local regulations.

Failure to attend the EOT visit exclusively due to a deteriorated clinical condition will not be considered a protocol deviation.

Any protocol deviation will also be discussed with the Investigator during monitoring visits.

7. STUDY ASSESSMENTS AND PROCEDURES

7.1 ELIGIBILITY ASSESSMENTS

The patient will be allocated a patient number in the e-CRF after signing the ICF and screening for eligibility begins. This patient number should be used on all future documentation and correspondence referring to this patient. During the screening period, the Investigator will assess the patient's eligibility for inclusion in the study by conducting the assessments summarized below.

Table 8. Screening period assessments.

	ASSESSMENT	TIME
1. Written informed consent	The informed consent process involves an explanation and discussion with the patient including time for questions and answers and culminates in signing and dating the consent form if the patient agrees. Document registration in the patient’s medical chart as well. Substudy participation is optional and requires a separate signed consent.	Before any study-specific procedures.
2. Medical and cancer history/ clinical examination	Demographic data (race/ethnicity [if permitted], age, sex). Medical history: Includes relevant conditions and syndromes that started before registration and are not ongoing (no signs or symptoms) at time of registration or are controlled and do not require evaluation for severity or causality. Also includes any event qualifying as serious occurring prior to registration. Cancer history: Primary diagnosis, response history, date of last confirmed PD, and all prior treatment (including cumulative dose of prior oxaliplatin, if any).	Within 28 days prior to registration.
	Physical examination: Including weight, height (for BSA calculation). Vital signs: HR, ABP, and temperature. ECOG performance status (Appendix 1).	Within 10 days prior to registration.
	Concomitant therapies: All Medications taken by the patient (including any not prescribed by the Investigator) should be documented with indication.	Within 14 days prior to registration.
3. Laboratory tests	Hematology: Complete blood count, differential WBC (neutrophils, lymphocytes), hemoglobin, and platelets. Biochemistry-A: ALP, AST, ALT, total bilirubin (and direct bilirubin if total is >1.5 x ULN), GGT, creatinine/CrCL (Cockcroft-Gault formula, Appendix 2), glucose, LDH, and serum electrolytes (Na ⁺ , K ⁺ , Total calcium). Biochemistry-B: Total proteins and albumin.	Within 10 days prior to registration.
4. Pregnancy test	Assessment of β-hCG only if the patient is a WOCBP (Appendix 3).	Within 7 days prior to registration.
5. Cardiac assessment	ECG: Including rhythm definition and PR interval; heart rate; QT interval (raw); QRS complex duration.. LVEF: ECHO or MUGA scan.	Within 28 days prior to registration.
6. Disease assessments	Clinical/radiological tumor assessment: Helical i.v. and oral contrast-enhanced CT-scan (if appropriate) for chest, abdomen and pelvis and other areas of suspected diseases. If i.v. contrast is contraindicated for the CT-scan, chest evaluation should be performed using non-contrast CT and abdomen/pelvis evaluation using gadolinium-enhanced MRI. Tumor markers alone or chest radiography alone are not sufficient to assess tumor burden.	Within 28 days prior to registration.
7. Adverse events	Only information on SAEs that occurred after signature of the informed consent is required before treatment start. Grading should be as per the NCI-CTCAE v.4.	Within 14 days prior to registration.
	PRO QLQs: Patients will be asked to complete the EORTC QLQ-CIPN20 and QLQ-C30.	Within 10 days prior to registration.

Registration=confirmation of eligibility and inclusion.

	ASSESSMENT	TIME
--	------------	------

Permitted windows for assessments before Day 1 of Cycle 1:

If physical examination, ECOG PS, vital signs, hematology/biochemistry were assessed >10 days before Day 1 of Cycle 1, the tests must be repeated within 2 days before the first study drug administration.

If pregnancy test was done >7 days before Day 1 of Cycle 1, the test must be repeated within 2 days before the first study drug administration.

If tumor assessments were done >28 days before Day 1 of Cycle 1, the tests must be repeated within 2 days before the first study drug administration.

A patient should only be treated if eligibility criteria are still met according to assessments performed closest to treatment start.

ABP, arterial blood pressure; AE, adverse event; ALP, alkaline phosphatase; ALT, alanine aminotransferase; AST, aspartate aminotransferase; β -hCG, beta subunit of human chorionic gonadotropin; BSA, body surface area; CrCL, calculated creatinine clearance; CT, computed tomography; ECG, electrocardiogram; ECHO, echocardiogram; ECOG, Eastern Cooperative Oncology Group; EORTC, European Organisation for Research and Treatment of Cancer; GGT, gamma-glutamyltransferase; HR, heart rate; IC, Informed Consent; IF, immunofixation; LDH, lactate dehydrogenase; LVEF, left ventricular ejection fraction; MRI, magnetic resonance imaging; MUGA, multiple-gated acquisition; NCI-CTCAE, National Cancer Institute Common Terminology Criteria for Adverse Events; PRO, patient reported outcomes; PS, performance status; QLQ, quality of life questionnaire; SAE, serious adverse event; ULN, upper limit of normal; WBC, white blood cells; WOCBP, woman of childbearing potential.

